## DOCUMENT HISTORY

Version	Author	Date	Reason
Draft V0.1	[REDACTED] [REDACTED]	February 28, 2018	Initial draft, based on Protocol Rev. A dated 19 Aug 2014 and eCRF dated 15 Jan 2018
Draft V0.2	[REDACTED] [REDACTED]	April 10, 2018	Comments from sponsor incorporated
Final V1.0	[REDACTED] [REDACTED]	April 20, 2018	Comments from sponsor incorporated and finalization

## LIST OF ABBREVIATIONS

6MWD	6 Minute Walk Test
AATD	Alpha-1 Antitrypsin Deficiency
AE	Adverse Event
BLVR	Bronchoscopic Lung Volume Reduction
BMI	Body Mass Index
CI	Confidence Interval
COPD	Chronic Obstructive Pulmonary Disease
CT	Computed tomography
DLCO	Diffusion Capacity of the Lung for Carbon Monoxide
eCRF	Electronic Case Report Form
FEV 1	Forced Expiratory Volume
FVC	Forced Vital Capacity
HRCT	High Resolution Computed Tomography
ITT	Intent-to-Treat population
LPS	Lung Perfusion Scintigraphy
LVR	Lung Volume Reduction
mMRC	Modified Medical Research Council
PT	Preferred Term
RV	Residual Volume
SAE	Serious Adverse Event
SAP	Statistical Analysis Plan
SD	Standard Deviation
SGRQ	St. George's Respiratory Questionnaire
SOC	System Organ Class
TLC	Total Lung Capacity
Tx1	RePneu procedure 1
Tx2	RePneu procedure 2
Tx3	RePneu procedure 3

## 1 INTRODUCTION

### 1.1 Scope of this Document

This Statistical Analysis Plan (SAP) describes the planned statistical analysis of the RePneu study CLN0017. The SAP is based on the relevant sections of the protocol revision A (dated 19 August 2014) and the annotated eCRF (electronic Case Report Form) (dated 15 January 2018). This SAP was prepared based on the AMS Standard Operating Procedure ST-02.01.

The SAP contains a more technical and detailed elaboration of the principal features of the analysis described in the protocol. It includes detailed descriptions for executing the statistical analyses of all variables and describes how analyses are to be presented.

This SAP addresses both the safety listings during the ongoing study and the final analyses (see section 2 for the types of analyses planned). All versions of the SAP will be filed in the trial master file. Summary of changes and justification for each revision will be recorded in the version history. The SAP version used for the final analysis will be finalized prior to data base lock.

### 1.2 Study Design

This CLN0017 Study is a prospective, multicenter, open label, single-arm study. The objective of this post-marketing study is to advance the understanding of mechanism of action of the CE marked RePneu Coil by observing changes in lung physiology and cardiac performance in patients with emphysema treated with the RePneu Coils, when used as intended.

Investigators will have been trained and/or re-trained in the proper use and operation of the RePneu System, and will have performed several commercial procedures prior to initiation of any treatment.

Subjects must meet all of the following inclusion criteria to be entered into the study:

1. Adult subjects diagnosed with emphysematous type of COPD.
2. CT scan indicates bilateral emphysema, with sufficient lung parenchyma for coil deployment (based on PneumRx CT scoring) criteria.
3. Subject has post-bronchodilator FEV1  $\leq 45\%$  predicted.
4. Subject has Total Lung Capacity  $> 100\%$  predicted.
5. Subject has residual volume (RV)  $\geq 175\%$  predicted.
6. Subject has marked dyspnea scoring  $\geq 2$  on mMRC scale of 0-4.
7. Subject read, understood and signed the Informed Consent form.
8. Subject has received Pneumococcal and Influenza vaccinations consistent with local recommendations and/or policy

Subjects will be excluded from the study if any of the following conditions apply:

1. Subject has co-morbidities that may significantly reduce subject's ability to improve exercise capacity (e.g. severe arthritis, planned knee surgery) or baseline limitation not due to dyspnea.
2. Subject has a change in FEV1 >20% (or, for subjects with pre-bronchodilator FEV1 below 1 L, a change of > 200 mL) post-bronchodilator unless investigator can confirm by other means that subject does not have asthma.
3. Subject has severe gas exchange abnormalities as defined by:
  - a) a. PaCO2 >55 mm Hg
  - b) b. PaO2 <45 mm Hg on room air (High altitude criterion: PaO2 <30 mm Hg)
4. Subject has severe pulmonary hypertension defined by right ventricular systolic pressure >50 mm Hg via right heart catheterization and/or echocardiogram.
5. Subject has evidence of other severe disease (such as, but not limited to, lung cancer or renal failure), which in the judgment of the investigator may compromise survival of the subject for the duration of the study.
6. Subject is pregnant or lactating, or plans to become pregnant within the study timeframe.
7. Subject has an inability to tolerate bronchoscopy under moderate sedation or general anesthesia.
8. Subject has clinically significant bronchiectasis.
9. Subject has had previous LVR surgery, lung transplantation, lobectomy or other BLVR treatment in either lung.
10. Subject has participated in studies to treat COPD using high dose radiation.
11. Subject has been involved in pulmonary drug or device studies within 30 days prior to this study.
12. Subject is chronically taking >20 mg prednisone (or equivalent dose of a similar steroid) daily.
13. Subject requires high level chronic immunomodulatory therapy to treat a moderate to severe chronic inflammatory autoimmune disorder.
14. Subject is on any type of antiplatelet or anticoagulant therapy which cannot be stopped for seven (7) days prior to procedure.
15. Subject has a sensitivity or allergy to Nickel.
16. Subject has a known sensitivity to drugs required to perform bronchoscopy.
17. Subject has been diagnosed with alpha-1 antitrypsin deficiency (AATD).
18. Subject has any other disease, condition(s) or habit(s) that would interfere with completion of study and follow-up assessments, would increase risks of bronchoscopy or assessments, or in the judgment of the investigator would potentially interfere with compliance to this study or would adversely affect study outcomes.

It was planned to enroll 60 patients into two sites which should be bilaterally treated. Due to an early termination of the study the total number of enrolled patients will not be as high as planned.

The follow up visits shall be performed 1 month post each procedure and then 3 months post final treatment. The final study follow up visit shall be performed 1 year post first treatment.

### **1.3 Objectives of the Study**

The objective of this post-marketing study is to advance the understanding of the mechanism of action of the CE marked RePneu Coil by observing changes in lung physiology and cardiac

performance in patients with emphysema treated with the RePneu Coils, when used as intended.

**Primary Endpoint:**

Changes at 3 months post final treatment and 12 months post first treatment in:

- 6 Minute Walk Distance (6MWD)

**Secondary Endpoints:**

Changes prior and post procedure at Tx1, Tx2 and optional Tx3 in:

- Geometry (roundness) of major lung airways as defined by the ratio of major versus minor diameter measured from 3 bronchoscopic still images prior and post procedure taken in the lobar airway of the carina leading to segmental airways or while in any segmental airways of the same lobe of the carina leading to sub-segmental airways)
- Static and dynamic pulmonary compliance measurement prior to and post treatment including closing volumes, closing capacity and small airways function

Changes at 3 months post final bilateral treatment and 12 months post first treatment in:

1. Physical activity and energy expenditure measured over a period of a week using multi-axial accelerometer.
2. Forced expiratory volume in one second (FEV1)
3. St. George's respiratory questionnaire (SGRQ)
4. Residual volume (RV)
5. Residual volume/total lung capacity (RV/TLC)
6. Diffusion capacity (DLCO)
7. mMRC dyspnea scale
8. Cardiovascular parameters such as heart rate, heart ejection fraction, systemic blood pressure
9. Body composition including BMI, fat per mass
10. Static and dynamic pulmonary compliance measurement using esophageal balloon

Changes at 12 months post first treatment in:

11. Ventilation and perfusion single photon emission tomography (V/P SPECT) or Quantitative lung perfusion scintigraphy (LPS)
12. Diaphragm position during exhalation (Comparison of diaphragm apex to rib landmarks using frontal HRCT)
13. Lung density distribution (post CT image data processing and reconstruction)

The study was prematurely terminated due to recruitment. Given the limited number of patients included in the database, the following data was not entered into the database and subsequently not analysed for the following endpoints:

1. Geometry (roundness) of major lung airways as defined by the ratio of major versus minor diameter measured from 3 bronchoscopic still images prior and post procedure taken in the lobar airway of the carina leading to segmental airways or while in any segmental airways of the same lobe of the carina leading to sub-segmental airways)
2. Static and dynamic pulmonary compliance measurement prior to and post treatment including closing volumes, closing capacity and small airways function
3. Physical activity and energy expenditure measured over a period of a week using multi-axial accelerometer.
4. heart ejection fraction, systemic blood pressure
5. fat per mass
6. Ventilation and perfusion single photon emission tomography (V/P SPECT) or Quantitative lung perfusion scintigraphy (LPS)
7. Diaphragm position during exhalation (Comparison of diaphragm apex to rib landmarks using frontal HRCT)
8. Lung density distribution (post CT image data processing and reconstruction)
9. St. George's respiratory questionnaire (SGRQ)

## 1.4 Overview of Assessments

The CLN0017 Study visits are planned as follows:

**Baseline Visit:** Participant agrees to be a part of the study and signs the informed consent. Baseline tests for primary and secondary endpoints will be performed. **Participant is evaluated and selected for RePneu procedure and has met inclusion/exclusion criteria.**

**First and Second Procedure visit:** **Participant undergoes the RePneu Procedure** in accordance with manufacturer Instructions for Use. Procedure data will be collected.

**Third Optional Procedure:** Patient will receive an additional 1-3 coils in each treated lobe, at the discretion of the treating investigator if the initial coil dose did not bring the expected benefit.

The procedures shall be performed no closer together than 4 weeks and if possible no longer than 8 weeks apart.

**Follow up Visit (s):** The follow up visits shall be performed 1 month post each procedure and then 3 months post final treatment. The final study follow up visit shall be performed 1 year post first treatment.

Follow-up visits will occur at the hospital in which the coil implantation procedure was performed.

An overview of the assessments can be found in Table 1.

**Table 1: Visit Schedule**

## 2 TYPES OF PLANNED ANALYSES

### 2.1 Final analysis

The final analysis shall consist of all analyses described in this document. The details of the analyses are described in section 4. Additionally, Appendix I: Overview of tables, figures and listings to be produced provides an overview of all tables, plots and listings to be produced as well as the appropriate analysis set.

### 2.2 Interim analyses

Interim analyses will not be performed for this study.

For data cleaning and quality purposes an overview of safety variables will be created in the form of an Excel listing monthly.

## 3 GENERAL ANALYTICAL CONSIDERATIONS

### 3.1 Analysis Set

The ITT population will include all subjects who have met the inclusion/exclusion study criteria defined in the protocol.

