### **3.3.2 Effectiveness and Safety Analyses**

The endpoints will be analyzed with a paired t-test, which will compare baseline to 3-month post final treatment and 12-months post first treatment follow-up values. A p-value of <0.05 will be considered statistically significant. Adverse events will be categorized into medically relevant categories and presented as frequency counts and percentages. All results tables and plots shall clearly display the total number of patients in the analysis set (N) and the number of patients with evaluable data (n).

Output designs or minor changes in the tables may be adapted to programming and/or sponsor demands.

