## 5.2.2 Protocol Deviation

A listing with information on protocol deviations will be provided, including:

- Inclusion/Exclusion Criteria not met
- Lost-to-follow-up
- Unilateral treatment
- 1 month post treatment 1 Visit not done
- 1 month post treatment 2 Visit not done
- 3 months post final treatment Visit not done
- 12 months post treatment 1 Visit not done

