### 5.3.1 Enrollment by site

A table showing the number and percentage of enrolled patients by site will be provided for the final analyses.

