## APPENDIX I: OVERVIEW OF TABLES, FIGURES AND LISTINGS TO BE PRODUCED

### Overview of planned tables

Programmer Note: Please adapt the numbering of subgroup tables as may be necessary.

Table Number	Title	Analysis Set for Final Analyses	Subgroup Analyses 
14.1.1	Patient accountability	ITT	No
14.1.2	Study terminations	ITT	No
14.2.1	Enrollment by site	ITT	No
14.2.2	Demographics	ITT	No
14.2.3	Baseline characteristics	ITT	No
14.2.4	Medical history	ITT	No
14.2.5	History and characterization of emphysema	ITT	No
14.2.6	Treatment of emphysema	ITT	No
14.3.1	Number of devices implanted	ITT	No
14.3.2	Procedure time	ITT	No
14.3.3	Post-procedure hospital stay	ITT	No
14.6.1	Adverse events	ITT	No
14.6.2	Serious adverse events	ITT	No
14.6.3	Device and procedure related adverse events	ITT	No
14.7.1	Change from baseline in 6MWT in m	ITT	No
14.7.2	Number and percentage of patients achieving change in 6MWT in m $\geq 25$	ITT	No

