### Overview of planned listings

Listing Number	Title	Analysis Set For Final Analyses
16.1	Study Patients	ITT
16.2	Protocol Deviation	ITT
16.3	Baseline Data	ITT
16.4	Procedural Data	ITT
16.4	Overview of safety variables	ITT
16.5	Overview of deaths	ITT
16.6	Overview of effectiveness variables	ITT

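### SAP 3.1 defines its only analysis set by eligibility and uses it for every safety output; read literally, a treated patient later found ineligible drops out of the AE tables and the death listing

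*SAP*

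**What the plan says.** SAP 3.1 is a single sentence: "The ITT population will include all subjects who have met the inclusion/exclusion study criteria defined in the protocol". It mentions neither enrolment nor treatment and is almost the study-population sentence of Protocol 4.3. SAP section 4, item 3, keeps unilaterally treated subjects in ITT and drops the per-protocol analysis. No treated or safety set is defined anywhere.

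SAP 2.1 gives Appendix I its authority: it "provides an overview of all tables, plots and listings to be produced as well as the appropriate analysis set". Every row there is marked ITT, including "Device and procedure related adverse events" (Table 14.6.3), "Overview of deaths" (Listing 16.5) and the deviation listing (16.2). SAP 3.3.2, which covers both effectiveness and safety, also requires results tables to show the size of the analysis set.

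SAP 5.2.2 requires the deviation listing to report "Inclusion/Exclusion Criteria not met". SAP 5.2.1 counts enrolled patients and patients in the analysis sets on separate lines.

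**The concern.** A set defined by having met the criteria cannot contain a subject who did not meet them. If Listing 16.2 is run on that set, one of its required categories can never have an entry. The same rule governs the AE, SAE and death outputs, so a patient who received coils and was afterwards found ineligible would be absent from them.

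In an implant study the safety outputs should cover everyone in whom a procedure was started, because the exposure does not depend on whether a criterion was misjudged. SAP 5.6.2 restricts the secondary effectiveness endpoints to listings, so the safety outputs carry much of the report. SAP 1.2 says that enrolment fell short of plan, and at small N one patient can change a rate visibly.

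**Working it through.** **Outputs tied to the set.** Appendix I has 16 tables + 1 figure + 7 listings = 24 rows, and 24 of 24 are marked ITT. Two listings share the number 16.4.

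**The two readings side by side.**

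- *Literal:* membership means that the criteria were in fact met. The eligibility category of SAP 5.2.2 is then always empty in Listing 16.2. Treated patients later found ineligible are left out of Tables 14.6.1 to 14.6.3 and Listing 16.5. Eligible subjects who never had a procedure are counted in the safety denominators.
- *Benign:* membership means judged eligible at enrolment. SAP 1.4 uses the phrase in that sense for the baseline visit: "Participant is evaluated and selected for RePneu procedure and has met inclusion/exclusion criteria". SAP 5.3.1 promises "A table showing the number and percentage of enrolled patients by site will be provided for the final analyses", and Appendix I runs that table on ITT. Nobody is lost on this reading.
- SAP 5.2.1 points the other way: two separate lines for enrolled and analysed patients suggest that the numbers can differ.

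**Size if the literal reading is programmed.** The documents do not give the final N; SAP 1.2 says only that it is below the planned 60. Assumptions: N treated patients, two procedures each, at most one event of a type per patient, and one treated patient excluded as ineligible. With k patients having the event, k/N becomes (k − 1)/(N − 1) if the excluded patient had it, or k/(N − 1) if not.

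Plausible values of k come from Protocol Table 2 (6-month SAEs per procedure). Its own percentages reproduce: 14/238 = 5.9% for pneumothorax and 41/238 = 17.2% for COPD exacerbation or pneumonia.

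- N = 10, 20 procedures: pneumothorax 14/238 × 20 = 1.2, so k = 1. The rate 1/10 = 10.0% becomes 0/9 = 0% or 1/9 = 11.1%.
- N = 10, exacerbation or pneumonia: 41/238 × 20 = 3.4, so k = 3. The rate 3/10 = 30.0% becomes 2/9 = 22.2% or 3/9 = 33.3%.
- N = 59, 118 procedures: pneumothorax 14/238 × 118 = 6.9, so k = 7. The rate 7/59 = 11.9% becomes 6/58 = 10.3% or 7/58 = 12.1%.

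On the benign reading, or if every treated patient was eligible, the change is zero at any N.

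**The case against.** The strongest reply is that the harmful reading is an inference. SAP 3.1 says whom the set includes; it does not say that it includes only them, or when and by whom eligibility is judged. Most of the SAP's own usage favours judgement at entry: SAP 1.4, the enrolment table on ITT, and the deviation listing itself, which suggests that the authors expected violators inside the set. Unilateral treatment is also a listed deviation in SAP 5.2.2, and SAP section 4 keeps those subjects, so being a deviator does not by itself remove anyone.

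Exposure is also limited. Protocol 4.7 exits ineligible subjects before treatment is scheduled, CT scoring is done by both sponsor and site (Protocol 4.7.2), and the investigator waits for the sponsor's CT feedback before treating (Protocol section 12).

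Much of this stands. The benign reading is plausible and may be what was meant, and the safeguards lower the chance that it matters. They do not settle the text. SAP 3.1 does not state the benign reading, and SAP 5.2.1 sits awkwardly with it. SAP section 4 revisits ITT membership but resolves only unilateral treatment. Protocol 4.7 does not cover ineligibility discovered after treatment, which source verification under Protocol section 10 could bring to light. Two programmers could build different sets from the same sentence.

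A reader might go further and infer that treated patients were in fact dropped, or that the safety rates are biased downwards. The documents show no such patient and order no such exclusion, and the rate can move either way.

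**Conclusion.** The point holds as a defect of definition that should be fixed. Followed literally, SAP 3.1 conflicts with SAP 5.2.2 and removes treated eligibility violators from the AE/SAE tables and the death listing; a plausible milder reading exists but is not written down. The conflict needs no assumption about the data. The numerical effect does: it requires at least one treated patient found ineligible and the literal reading in the program. On the assumptions above, one exclusion at N = 10 moves a 10.0% rate to 0% or 11.1%; at N = 59 it moves 11.9% to 10.3% or 12.1%. It may be zero.

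Three stronger conclusions are not supported:

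- Protocol 4.5 is not contradicted, because it governs the collection of adverse events, not the set on which they are tabulated.
- The AE listing of SAP 5.5 has no clearly matching row in Appendix I and the device-removal listing of SAP 5.5.5 has none. That does not cancel them, since SAP 2.1 makes every analysis described in the SAP part of the final analysis.
- Nothing here shows that the baseline or effectiveness outputs need a different population.

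**What to change.** 1. Add to SAP 3.1 that eligibility is as judged at enrolment, and that neither a violation found later nor unilateral treatment removes a subject from ITT. Baseline and effectiveness outputs stay on this clarified set.
2. Define a safety set: all subjects in whom at least one coil procedure was started, regardless of eligibility. Assign it to Tables 14.6.1 to 14.6.3, Listing 16.5, and the AE and device-removal listings, and give those two listings rows in Appendix I. List AEs and deaths of enrolled but untreated subjects separately, so that events collected from study entry under Protocol 4.5 are still reported.
3. Run accountability (Table 14.1.1 and its figure), terminations (14.1.2), enrolment by site (14.2.1) and Listings 16.1 and 16.2 on all enrolled subjects.
4. Record the change in SAP section 4.

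The cost is SAP wording, Appendix I entries and one flag variable derived from the procedure dates that SAP 5.5 already lists. No new data are needed. Reported rates may shift slightly in either direction, or not at all.

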### 3.2 Subgroup Analyses

No Subgroup Analyses will be done for this study.

### 3.3 Analytical Methods

The analysis will be performed in SAS® (version 9.4. or higher).

#### 3.3.1 Descriptive statistics

Continuous variables will be displayed including arithmetic mean, standard deviation (SD), minimum (min), median and maximum (max). Additionally, the number of patients in the analysis set (ITT), those contributing to the analysis (N) and the number of patients not included in the analysis due to missing data (missing) will be displayed.

The Change from Baseline will be calculated for each patient individually and averaged for values at baseline (mean, SD, min, median, max at baseline), values at each visit (mean, SD, min, median, max at visit) and the change from baseline to each visit.

Categorical variables will be displayed as frequencies and percentages (i.e. absolute and relative frequencies). If not specified otherwise, the percentages will be based on all patients respectively procedures available for analysis (non-missing and missing). The number of patients with missing data will also be summarized.

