## **3.4 Missing/Inconsistent Data**

### **3.4.1 Imputation**

Analyses will be based upon observed data without imputation.

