## 5.3 Baseline Data

Continuous data will be summarized using descriptive statistics (mean, SD, min, median, max). Additionally, the number of patients included in the patient set (N), number of patients contributing to the analysis (n) and the number of patients not included in the analysis due to missing data (missing) will be displayed.

Categorical variables will be displayed as frequencies (p/n) and percentages (i.e. absolute and relative frequencies). Unless otherwise noted, percentages will be based on the patients available for analysis (non-missing). The number of patients with missing data will be also be summarized.

All baseline analyses will be based on the Intention-to-treat Set (ITT).

Furthermore, all of the baseline data mentioned in the following subsections 5.3.1-5.3.6 including text specifications will be listed.

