### **5.6.1 Primary effectiveness endpoint**

Changes at 3 months post final treatment and 12 months post first treatment in:

- Minute Walk Distance (6MWD)

The change from baseline as continuous variable and the responder analysis as categorical variable will be presented.

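### Does the 6MWD responder percentage in SAP Table 14.7.2 fall under two conflicting denominator rules?

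*SAP*

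**What the plan says.** SAP 5.6.1 announces two presentations of the primary endpoint: "The change from baseline as continuous variable and the responder analysis as categorical variable will be presented". SAP 5.6 sets the responder threshold at a gain of at least 25 m. Appendix I assigns both tables, 14.7.1 for the mean change and 14.7.2 for responders, to the ITT set. The title of the second begins "Number and percentage of patients achieving change in 6MWT in m". Neither 5.6.1 nor Appendix I names a denominator.

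Three other places in the SAP bear on the denominator:

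- **3.3.1** gives the default for categorical variables, which holds unless another rule is stated: "the percentages will be based on all patients respectively procedures available for analysis (non-missing and missing"). It also requires the number of patients with missing data to be reported.
- **3.4.1**, headed Imputation, says: "Analyses will be based upon observed data without imputation".
- **5.3**, which covers baseline data only, says that "percentages will be based on the patients available for analysis (non-missing").

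SAP 3.3.2 requires every results table to show "the total number of patients in the analysis set (N) and the number of patients with evaluable data (n"). SAP 3.1 defines the analysis set by eligibility: "The ITT population will include all subjects who have met the inclusion/exclusion study criteria defined in the protocol". Among the deviations to be listed, SAP 5.2.2 includes "12 months post treatment 1 Visit not done".

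**The concern.** A mean change can be computed only for patients with a walk test at both baseline and the visit. Under the 3.3.1 default, the responder percentage is divided by everyone in the ITT set. Two tables for the same endpoint therefore rest on different patients, and a missing test counts in effect as non-response without the SAP saying so. Set beside 3.4.1, this looks like a contradiction. A programmer who took 3.4.1 as the guide would divide by the observed patients and print a different figure.

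Missing tests are to be expected. The ITT set requires neither treatment nor a follow-up visit, SAP section 4 brings in patients treated on one side only, and 5.2.2 foresees missed visits. If more patients miss the 12-month visit than the earlier one, the responder percentage would fall between visits even if response among those tested did not change. Since the secondary endpoints are only listed, these are the only two effectiveness tables planned.

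**Working it through.** **Which rule applies.** The responder analysis is labelled categorical in 5.6.1, so it falls under 3.3.1. That default yields only to a rule stated elsewhere. The one stated exception, in 5.3, is confined to baseline data. Section 3.4.1 forbids filling in values and does not mention percentages. Leaving a patient in the denominator and reporting that patient as missing assigns no walk distance to anyone, so 3.3.1 and 3.4.1 can both be followed. On the text, Table 14.7.2 has one denominator: all ITT patients.

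**Size of the gap.** The documents give no responder rate, missing rate or final sample size, so there is no figure of the plan's own to reproduce. Let p be the response rate among patients tested and m the fraction missing. Both are assumed.

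- Observed denominator: p
- All-patient denominator: p × (1 − m)
- Gap: p − p × (1 − m) = p × m

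| p (assumed) | m = 10% | m = 20% | m = 40% |
|---|---|---|---|
| 30% | 27% (gap 3) | 24% (gap 6) | 18% (gap 12) |
| 50% | 45% (gap 5) | 40% (gap 10) | 30% (gap 20) |
| 70% | 63% (gap 7) | 56% (gap 14) | 42% (gap 28) |

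Cells show the all-patient percentage, with the gap in points. With no missing data the gap is zero.

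**Apparent fading, and whether a reader could see it.** Take N = 20 (assumed), with 2 missing at the early visit and 8 at 12 months.

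- Among those tested: 9/18 = 50%, then 6/12 = 50%.
- Among all patients: 9/20 = 45%, then 6/20 = 30%, a drop of 15 points.

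The counts required by 3.3.1 and 3.3.2 would show N = 20 with n = 18 and then n = 12. Dividing 9 by 18 and 6 by 12 gives 50% at both visits. The listing described in 5.6 (Listing 16.6) also shows each patient's walk distance, change and responder status by visit.

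**What the full-set figure means.** At 12 months in this example the 8 missing results could lie anywhere from no responders to all responders, which gives 6/20 = 30% to (6 + 8)/20 = 70%. The full-set percentage is the lower end of that range. The observed percentage, 50%, lies inside it and is right for the whole set only if the missing patients respond at the same rate as those tested.

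**Precision.** Exact 95% intervals are 21–79% for 6/12 and 12–54% for 6/20. With N = 10 and 2 missing they are 16–84% for 4/8 and 12–74% for 4/10.

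**The case for a change.** The best argument for a change is that the SAP never says missing is meant to count as non-response, so a result shown under the primary endpoint would carry that assumption without a label. The drafting is also uneven. Sections 3.3.1 and 5.3 describe the denominator in nearly the same terms with opposite meanings. In 3.3.1, under continuous variables, N stands for patients contributing data, whereas in 3.3.2 it stands for the whole analysis set. One sentence and one extra table line would cost almost nothing.

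Part of this stands. The choice is unstated, and the two tables do rest on different patients. The rest carries less weight. The differing wording in 5.3 shows that the SAP states an exception where it wants one. The conflicting use of N can be settled from the missing count, which is required in any case. A second line giving the other percentage would add nothing that N, n and the number of responders do not already give. Nor is the observed percentage clearly better, because it looks too favourable if patients who do badly miss their visits.

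**Conclusion.** No change to the plan is needed. There is one denominator rule for Table 14.7.2, and it does not contradict the no-imputation rule. What remains is a choice of presentation that the SAP leaves unexplained. It could move the printed percentage by 5 to 20 points if 50% of tested patients respond and 10 to 40% are missing, or by 3 to 28 points if response is allowed to run from 30% to 70%. All of these inputs are assumptions.

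The choice does not touch the planned inference. The protocol's primary endpoint is the change in 6MWD (section 3), and both documents test it with a paired t-test (protocol 4.6, SAP 3.3.2), which the responder denominator does not enter. The responder table was added in the SAP and has no test or decision attached. The study stopped early with few patients, and in the small-sample examples the intervals under the two denominators overlap heavily. A full-set denominator is the cautious reading of incomplete data, and the counts printed with it let anyone obtain the other. An analyst who footnotes the denominator in the table will have done all that is needed.
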